See [Table 1-9](#) for assessment notes and abbreviation definitions.

Table 1-7. Schedule of Activities: Part 5B (AML) Conventional Dosing – Regimen 1 (Days 1 Through 3 In Week 1 And BIW In Weeks 2 And 3 Only)

Weeks in Cycle	Treatment Cycles 5+												LTFU/EOOS
	Q4W												
Days	D1	D2-3	D4-7	D8	D9	D10	D15	D16	D17	D22	D23	D24	EOT
Hours (relative to start of dosing)													
GENERAL AND SAFETY ASSESSMENT													
Informed consent													
Clinical evaluation	X	X			X	X		X			X	X	
Vital signs	X	X	X	X	X	X	X	X	X	X	X	X	X
12-lead ECG	X	X	X	X	X	X	X	X	X	X	X	X	X
ECHO/MUGA													
TLS prophylaxis	X	X			X	X							X
Prior / Conmed reporting													X
AE / SAE reporting													X
Subsequent anti-cancer therapy & Survival													X
STUDY TREATMENT													
AMG 176 dosing	X	X		X	X			X		X			
Azacitidine dosing	X	X	D4-5	X	X								
LABORATORY ASSESSMENTS													
Local Labs													
Safety lab tests	X	X		X	X			X		X	X		X X
TLS monitoring test	X	X	X	X	X	X	X	X	X		X		
Cardiac monitoring tests	X	X		X	X	X		X	X	X	X	X	X X X
Pregnancy test	X												X X
Hepatitis serology													
Central Labs													
Biomarker - PBMC													X
Bone marrow aspirate/biopsy													
C2D1, C3D1, and thereafter prior to every other cycle or when clinically indicated until disease progression and to confirm CR and MRD status													
DISEASE AND IMAGING ASSESSMENTS													
Bone marrow aspirate/biopsy													
Peripheral blood count	X			X			X			X			X
Overall disease response													
Assessed and documented at every cycle and at time of PD													

Page 3 of 3

See Table 1-9 for assessment notes and abbreviation definitions.

CONFIDENTIAL

AMGEN®

Table 1-8. Schedule of Activities: Part 5B (AML) Conventional Dosing – Regimen 2 (Days 1 Through 5 In Week 1 and BIW In Week 2 Only)

Weeks in Cycle	Screen	Treatment Cycle 1														W4			
		W1				W2				W3			D22		D23	D24			
Days	D-14 to D0	D1	D2-5	D6-7	D8	D9	D10	D15	D16	D17	D22	24h after D16	8	EOI	EOI	EOI	EOI		
Hours (relative to start of dosing)																			
GENERAL AND SAFETY ASSESSMENT																			
Informed consent	X																		
Clinical evaluation	X	X																	
Vital signs	X	X	X																
12-lead ECG	X	X	X	X	X	X	X	X	X	X	X	X	X	X	X	X	X	X	
ECHO/MUGA	X																		
Hospitalization		Hospitalization days (Days 1 through 4)																	
TLS prophylaxis	X																		
Prior / Conned reporting																			
AE / SAE reporting																			
Subsequent anti-cancer therapy & Survival																			
STUDY TREATMENT																			
AMG 176 dosing		X																	
Azacitidine dosing		X																	
LABORATORY ASSESSMENTS																			
Local Labs																			
Safety lab tests	X	X																	
TLS monitoring test	X	X	X	X	X	X	X	X	X	X	X	X	X	X	X	X	X	X	
Cardiac monitoring tests	X	X																	
Pregnancy test	X	X																	
Hepatitis serology	X																		
Central Labs																			
AMG 176 PK		X	X	X	X	X	X	X	X	X	X	X	X	X	X	X	X	X	
Azacitidine PK		X	X	X	X	X	X	X	X	X	X	X	X	X	X	X	X	X	
DISEASE AND IMAGING ASSESSMENTS																			
Bone marrow aspirate/biopsy	X																		
Peripheral blood count	X	X																	
Overall disease response																			
Assessed and documented at every cycle and at time of PD																			

Page 1 of 3

See [Table 1-9](#) for assessment notes and abbreviation definitions.

Table 1-8. Schedule of Activities: Part 5B (AML) Conventional Dosing – Regimen 2 (Days 1 Through 5 In Week 1 and BIW In Week 2 Only)

Weeks in Cycle	Treatment Cycle 2-4														24h after D23
	W5-16														
Days	D1	D2-5	D6-7	D8	D9	D10	D15	D16	D17	D22	D23	D24			
Hours (relative to start of dosing)	pre-dose			24h after D8/pre-dose		24h after D9				pre-dose			24h after D16		
GENERAL AND SAFETY ASSESSMENT															
Informed consent															
Clinical evaluation	X			X		X		X			X		X		X
Vital signs	X	X		X	X		X	X			X	X	X	X	X
12-lead ECG	X	X	X	X	X	X	X	X	X	X	X	X	X	X	X
ECHO/MUGA															
TLS prophylaxis	X			X			X								
Prior / Commed reporting															
AE / SAE reporting															
Subsequent anti-cancer therapy & Survival															
STUDY TREATMENT															
AMG 176 dosing	X			X		X		X							
Azacitidine dosing	X			X		X		X							
LABORATORY ASSESSMENTS															
Local Labs															
Safety lab tests	X			X		X		X			X		X		X
TLS monitoring test	X	X	X	X	X	X	X	X	X	X	X	X	X	X	X
Cardiac monitoring tests	X		X	X		X	X	X	X	X	X	X	X	X	X
Pregnancy test	X														
Hepatitis serology															
Central Labs															
AMG 176 PK	X	X	X	X	X	X	X	X	X	X	X	X	X	X	X
Bone marrow aspirate/biopsy															
C2D1, C3D1, and thereafter prior to every other cycle or when clinically indicated until disease progression and to confirm CR and MRD status															
DISEASE AND IMAGING ASSESSMENTS															
Bone marrow aspirate/biopsy															
C2D1, C3D1, and thereafter prior to every other cycle or when clinically indicated until disease progression and to confirm CR and MRD status															
Peripheral blood count	X						X				X		X		
Overall disease response															
Assessed and documented at every cycle and at time of PD															

See [Table 1-9](#) for assessment notes and abbreviation definitions.

Table 1-8. Schedule of Activities: Part 5B (AML) Conventional Dosing – Regimen 2 (Days 1 Through 5 In Week 1 and BIW In Week 2 Only)

Weeks in Cycle	Treatment Cycle 2-4														24h after D 23	
	W5-16															
Days	D1	D2-5			D6-7	D8	D9			D10	D15	D16	D17	D22	D23	D24
Hours (relative to start of dosing)	pre-dose	0	12	24h after D5/ pre-dose	0	8	0	5	7	12	0	8	0	8	0	8
GENERAL AND SAFETY ASSESSMENT																
Informed consent																
Clinical evaluation	X				X					X				X		X
Vital signs	X	X			X	X			X	X			X	X	X	X
12-lead ECG	X	X	X	X	X	X	X	X	X	X	X	X	X	X	X	X
ECHO/MUGA																
TLS prophylaxis	X				X				X							
Prior / Commed reporting																
AE / SAE reporting																
Subsequent anti-cancer therapy & Survival																
STUDY TREATMENT																
AMG 176 dosing	X				X				X				X			
Azacitidine dosing	X				X				X				X			
LABORATORY ASSESSMENTS																
Local Labs																
Safety lab tests	X				X				X				X		X	X
TLS monitoring test	X	X	X	X	X	X	X	X	X	X	X	X	X	X	X	X
Cardiac monitoring tests	X		X	X		X	X	X	X	X	X	X	X	X	X	X
Pregnancy test	X															
Hepatitis serology																
Central Labs																
AMG 176 PK	X	X	X	X	X	X	X	X	X	X	X	X	X	X	X	X
Bone marrow aspirate/biopsy																
C2D1, C3D1, and thereafter prior to every other cycle or when clinically indicated until disease progression and to confirm CR and MRD status																
DISEASE AND IMAGING ASSESSMENTS																
Bone marrow aspirate/biopsy																
C2D1, C3D1, and thereafter prior to every other cycle or when clinically indicated until disease progression and to confirm CR and MRD status																
Peripheral blood count	X								X				X		X	
Overall disease response																
Assessed and documented at every cycle and at time of PD																

Page 3 of 3

See [Table 1-9](#) for assessment notes and abbreviation definitions.

Table 1-9. Schedule of Activities Notes and Abbreviation Definitions

Clinical evaluations: Physical exam, ECOG status, and weight will be collected pre-dose on dosing days. Medical and surgical history, height and neuropathy assessment (for MM subjects only) need only be collected at the screening visit. Prior to dosing on day 1 of every cycle, BSA must be calculated.
ECG: ECGs will be performed at the timepoints in the SOA as follows: Screening ECGs: Single ECG Baseline (pre-dose cycle 1 day 1): Three baseline ECGs will be collected approximately 15 minutes apart (\pm 5 minutes), with each baseline ECG in triplicate run consecutively (ie, all 3 ECGs should be completed within a total of 5 minutes from the start of the first to the completion of the third) for a total of 9 ECGs Cycles 1 through 4: Triplicate ECGs run consecutively (ie, all 3 ECGs should be started with \pm 5 minutes of infusion and be completed within a total of 5 minutes from the start of the first to the completion of the third) Cycle 5 and all subsequent cycles: Single ECG For Part 4 Cohorts 5a and 5b as well as Part 5A, 12-lead ECG assessments for C1D4 through D7 are optional based on investigator discretion.
ECHO or MUGA: Additional ECHO/MUGA, cardiac imaging and cardiac assessments are to be conducted if any clinical signs or symptoms of cardiomyopathy or other cardiac compromise are noted. If an ECHO or MUGA was performed within 4 weeks of C1D1 as part of standard of care, then it does not have to be repeated during screening as long as the same modality is used throughout the study. During LTFU and ECHO/MUGA is only required at the first LTFU visit.
Hospitalization for TLS monitoring and prophylaxis: All subjects will be hospitalized to monitor for TLS. Hospitalization will begin within 24 hours before the first dose of AMG 176 and continue until 24 hours post first AMG 176 dose for subjects on the AMG 176 QW schedule (Parts 1b, 3b, and 4) or post second dose of AMG 176 for subjects on the BIW schedule (Parts 1a and 3a). Hospitalization period can be increased per institutional standards or investigators discretion.
TLS Prophylaxis: See Section 6.1.4.1 for prophylaxis requirements including additional serum chemistry and hematology laboratory samples that must be collected within 24 hours prior to the first dose, and electrolyte values must be within normal range prior to AMG 176 dosing. Hospitalization for the purpose of TLS prophylaxis will not be captured as a Serious Adverse Event (SAE).
Peripheral Neuropathy Assessment: For MM subjects a peripheral neuropathy assessment will be performed at screening, on treatment if clinically indicated and then at the SFU visit. A neurological examination does not need to be performed by a neurologist, but should be performed by a qualified professional with knowledge and experience performing a neurological exam.
Patient Interview Substudy – Parts 3b, 4, and 5: Approximately 10 AML subjects from Parts 3b, 4, and 5 at select sites in countries where English is the primary language will be asked to participate in a Patient Interview Substudy (one 60-minute interview). The interview will take place as soon as possible after the completion of cycle 1, excluding days on which AMG 176 is administered and days on which subjects are hospitalized.

Table 1-9. Schedule of Activities Notes and Abbreviation Definitions (continued)

AMG 176 dosing: AMG 176 will be administered IV BIW (day 1 and 2, Weeks 1, 2, and 3) or QW (day 1, Weeks 1, 2, 3, [and 4]) depending on the Part and cohort the subject is enrolled in. A ramp-up dose of 120 mg/m ² will be required if the target dose is \geq 180 mg/m ² . AMG 176 will be infused for 2 hours (\pm 5 minutes).
For Part 3d: After week 3 subjects may crossover to Part 3b or Part 4 for continued treatment if approved by the investigator and Amgen medical monitor. Subjects from Part 3d who crossover to Part 3b will not crossover (for a second time) to Part 4.
For Part 5B (conventional dosing): Dosing will be AMG 176 on 3 consecutive days the first week, and BIW on weeks 2 and 3 each cycle in the first 6 subjects (regimen 1). If this schedule is deemed safe by the DLRT, the next 6 subjects will receive AMG 176 on 5 consecutive days the first week, and BIW dosing week 2 for each cycle (Regimen 2).
Azacitidine: Azacitidine will be co-administered with AMG 176 to subjects enrolled in Parts 4 and 5. Azacitidine will be administered at a dose of 75 mg/m ² IV or SC daily for the first 7 days of a 28-day cycle.
Oral itraconazole capsules (200 mg) will be given once daily (QD) for 7 days, starting at 8 am (\pm 1 hour) on day -3 through day 4 (last dose of itraconazole will be on day 4). Itraconazole dosing on day 1 should be at approximately the same time (\pm 5 minutes) as the start of infusion of AMG 176.
Safety Labs: Safety labs include chemistry, hematology, urinalysis, and coagulation analytes. See Table 11-1 for the list of analytes. Pre-dose safety labs are to be collected per the SOA and can be collected up to approximately 24 hours before treatment begins unless otherwise indicated (eg, TLS monitoring test).
TLS monitoring test: TLS monitoring tests consists of the chemistry analytes serum potassium, phosphorous, calcium, uric acid, and creatinine and will be performed at the timepoints in the SOA. The pre-dose samples must be collected within 4 hours before AMG 176 administration to ensure electrolytes are within normal range. Note: The pre-dose safety chemistry and TLS monitoring tests can be drawn at the same time provided they are collected within 4 hours before AMG 176 administration. For the BIW schedule, the D1 24-hour post-dose and the D2 pre-dose TLS monitoring test can be drawn at the same time.
For Part 4 Cohorts 5a and 5b as well as Part 5A, TLS monitoring test for C1D4 through D7 are optional based on investigator discretion.
Cardiac monitoring tests: Cardiac monitoring tests include the following analytes: troponin (I or T), creatine kinase-muscle/brain (CK-MB), and N-terminal prohormone of brain natriuretic peptide (NT-pro-BNP). These cardiac monitoring tests will be collected at the time points specified in the SOA and analyzed locally. In addition, samples will need to be submitted to the central lab. Refer to the central lab manual.
For Part 4 Cohorts 5a and 5b as well as Part 5A, cardiac monitoring tests for C1D4 through D7 are optional based on investigator discretion.

Table 1-9. Schedule of Activities Notes and Abbreviation Definitions (continued)

Pregnancy test (serum or urine). Applies to females of childbearing potential and will be performed locally at screening, prior to each treatment cycle (pre-dose), end of treatment, and at the safety follow-up visit.
PK: PK samples should be collected at the exact nominal time point as noted. Timepoints shown in the schedule of activities are relative to start of dosing of the corresponding treatment: AMG 176 or azacitidine. For pre-dose PK sample, the sample should be collected within 1 hour before the dose. For all other timepoints, PK samples should be collected within \pm 15 min of the designated time points. If unable to collect a PK sample at the specified nominal time point, then collect the sample as close as possible and record the actual collection time. Note: It is important to document the exact date and time of investigational product administration and PK sample collection.
AMG 176 PK: Samples collected and analyzed for AMG 176 at the timepoints indicated for cycle 1. Note: In the event that one or more additional step-doses are administered, PK should be collected at the following time points for the first two doses at the target dose: pre-dose, EOI, hour 3, hour 5, hour 7, hour 8, and hour 12 relative to the start of the target doses. All AMG 176 timepoints are relative to start of infusion.
Azacitidine PK: Samples collected and analyzed for azacitidine at pre-dose, EOI (10-40 min for IV or 30 min for SC), and 4 and 8 h after the start of IV infusion or following the SC dose of azacitidine.
For Part 4 Cohorts 5a and 5b as well as Part 5A, AMG 176 PK assessments for C1D4 through D7 are optional based on investigator discretion.
Optional Pharmacogenetics - saliva: For subjects who consent to the pharmacogenomics portion of the study, a saliva sample will be collected for extraction of DNA. These collections will not be requested for subjects in Japan.
Multiple myeloma Disease Assessments: Refer to Section 8.2.2.1
AML Disease Assessments: Refer to Section 8.2.2.2
EOT and SFU: In any case of premature treatment discontinuation, the investigator should make every effort to perform all examinations scheduled for the EOT and SFU visits. These data should be recorded, as they comprise an essential evaluation that should be performed prior to removing any subject from treatment and to allow for the evaluation of the study endpoints. The EOT visit will occur upon the decision to end the treatment (eg, due to intolerable adverse event [AE], disease progression). The SFU visit will occur 30 days (+3 days) after last dose of protocol-required therapies.
Note: If a subject withdraws consent, it is important to distinguish between withdrawal of consent from treatment (partial withdrawal of consent) which will allow for continued follow-up in LTFU (eg, for survival) or withdrawal of consent from study (full consent withdrawal). These discussions should be thoroughly documented in the subjects medical records.

Table 1-9. Schedule of Activities Notes and Abbreviation Definitions (continued)

LTFU/EOS: Long-term follow-up (LTFU) visits will occur every 3 months (\pm 14 days) for up to 1 year after EOT. The EOS for a subject will occur when the subject completes the LTFU or dies, whichever occurs first. During LTFU, all SAEs that the investigator becomes aware of, regardless of whether they are or are not suspected to be related to the investigational product, will be reported to Amgen. All serious adverse events (regardless of causality) shall be reported to Amgen immediately and no later than 24 hours after the investigator first becomes aware of the event.

Note: If a subject withdraws consent, it is important to distinguish between withdrawal of consent from treatment which will allow for continued follow-up in LTFU (eg, for survival) or withdrawal of consent from study. These discussions should be thoroughly documented in the subjects' medical records.

AE = adverse event; ALT = alanine aminotransferase; AML = acute myeloid leukemia; ANC = absolute neutrophil count; AST = aspartate aminotransferase; BIW = twice weekly; BNP = B-type natriuretic protein; BSA = body surface area; CBC = complete blood count; CR = complete response; CT = computed tomography; CXDX = cycle X day X; D = day; ECG = electrocardiogram; ECHO = echocardiogram; ECOG = Eastern Cooperative Oncology Group; EOI = end of infusion; EOS = end of study; EOT = end of treatment; FDG = fluorodeoxyglucose; [REDACTED]; G-CSF = granulocyte-colony stimulating factor; GGT = gamma-glutamyl transferase; h = hour; HBcAb = hepatitis B core antibody; HBsAg = hepatitis B surface antigen; HBV = hepatitis B virus; HCVAb = hepatitis C virus antibody; Ig = immunoglobulin; INR = international normalized ratio; LDH = lactate dehydrogenase; LFT = liver function test; LTFU = long-term follow-up; MCH = mean cell hemoglobin; MCHC = mean cell hemoglobin concentration; MCV = mean cell volume; min = minute; MM = multiple myeloma; MRD = minimal residual disease; MUGA = multigated acquisition scan; NaHep = sodium heparin; PBMC = peripheral blood mononuclear cell; PD = pharmacodynamics; PET = positron emission tomography; PK = pharmacokinetics; PT = prothrombin time; PTT = partial thromboplastin time; Q4W = every 4 weeks; Q8W = every 8 weeks; QTc = QT interval corrected; RBC = red blood cell; SAE = serious adverse event; SC = subcutaneous; Screen = Screening; SFLC = serum-free light chain; SFU = safety follow-up; SOA = schedule of activities; SPEP = serum protein electrophoresis; TBA = total bile acid; TLS = tumor lysis syndrome; UPEP = urine protein electrophoresis; W = week

2. Introduction

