6.2.2.2.4 Management of Renal Toxicities

Renal dysfunction is one of the MM-related organ/tissue dysfunction. Renal function must be monitored closely during treatment with AMG 176. Serum chemistry values, including blood urea nitrogen (BUN), serum creatinine, and urine for urinalysis and microscopic exam (microscopic exam only needed for positive dipstick), must be obtained and reviewed prior to each dose of AMG 176 per the schedule of assessments (see Section 1.3). AMG 176 must be held for subjects with CrCl or estimated glomerular filtration rate $< 30 \text{ mL/min}/1.73 \text{ m}^2$ or any other grade 3 or 4 renal toxicity any time during study treatment participation. Management should be tailored to the appropriate treatment for the underlying renal disorder according to the local SOC and institutional guidelines. AMG 176 can be restarted when the toxicity has improved to at least a grade 2.

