8.2.3 Safety Assessments

Planned time points for all safety assessments are listed in the Schedule of Activities see (Section 1.3).

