- To include omitted pages in Table 1-7 (Schedule of Activities: Part 5B acute myeloid leukemia [AML] Conventional Dosing – Regimen 1) and Table 1-8 (Schedule of Activities: Part 5B [AML] Conventional Dosing – Regimen 2) from amendment 15 to clarify that hospitalization is only required in the first cycle and to indicate the procedures for cycle 2 and beyond. This update allows to monitor safety without overburdening the clinical site and subject with unnecessary procedures.
- Minor updates in the list of references (Section 10).
- In addition, administrative and editorial changes (including grammatical, typographical, and formatting) have been made throughout the protocol.

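### Page 3 of the Regimen 2 schedule (Protocol Table 1-8) repeats cycles 2-4, leaving no scheduled timepoints for cycle 5 onward, end of treatment, safety follow-up or long-term follow-up

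*Protocol*

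**What the plan says.** Protocol Section 1.3 gives each Part 5B regimen its own schedule. Table 1-7 (Regimen 1) has pages for cycle 1 and cycles 2-4. Its third page is headed "Treatment Cycles 5" with a plus sign, and carries end-of-treatment and long-term follow-up columns. Table 1-8 (Regimen 2) has cycle 1 on its first page. Its second and third pages are both headed "Treatment Cycle 2-4", both labelled weeks 5 to 16, and both list days 1 to 24.

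The rest of the protocol takes its timing from this grid. Section 8.2.3 states: "Planned time points for all safety assessments are listed in the Schedule of Activities". In Table 1-9, "ECGs will be performed at the timepoints in the SOA as follows", with the later rule "Cycle 5 and all subsequent cycles: Single ECG". For troponin, CK-MB and NT-pro-BNP the same table says: "These cardiac monitoring tests will be collected at the time points specified in the SOA and analyzed locally". Section 8.2.5 sends laboratory timing to the Schedule as well, and the opening of Section 8 makes adherence to it mandatory.

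The rationale for Amendment 16 says that pages were added to Tables 1-7 and 1-8 "to indicate the procedures for cycle 2 and beyond". That shows what the pages were for. The point itself rests on the current tables.

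**The concern.** Section 2.3.2 names increased troponin as an identified risk, mitigated by a cardiac monitoring plan. Section 6.2.2.1 ties withholding and permanent discontinuation of AMG 176 to central troponin results. Those rules can act only on samples that are drawn, and for Regimen 2 the schedule of draws stops at week 16. Section 4.3.2 supports the conventional schedule with preclinical data and preliminary PK modelling. The modelled 5-days-on, 2-days-off regimen has a median weekly AUC 1.9 times that of BIW dosing at 240 mg/m².

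Treatment beyond week 16 is expected. Section 4.5.2 anticipates 6 months, and Section 9.4.1.2 sets the primary analysis at the opportunity to complete 6 cycles. The troponin summary over time in SAP Section 9.6.3 would have no scheduled Regimen 2 values after week 16. Subjects who stop earlier are affected too, because they pass through end of treatment and safety follow-up, for which Table 1-8 has no column.

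**Working it through.** **1. Is it only a mistyped header?** With 28-day cycles, cycle k covers weeks 4(k − 1) + 1 to 4k. Cycle 2 starts at week 4 × 1 + 1 = 5 and cycle 4 ends at week 4 × 4 = 16. The cycle label and week label on page 3 therefore agree. A correct third page would start at week 4 × 4 + 1 = 17. Page 3 also keeps the AMG 176 PK row, which Table 1-7 drops from cycle 5. The page repeats the cycles 2-4 block; it is not a cycle 5 page with a wrong number.

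**2. Dosing that falls outside the grid.** Section 6.1.1 gives 7 AMG 176 doses per cycle for the conventional scheme. This is reproduced: Regimen 2 is 5 + 2 = 7 and Regimen 1 is 3 + 2 + 2 = 7. For comparison, BIW is 2 × 3 = 6 and QW is 4. A subject completing 6 cycles receives 2 × 7 = 14 planned Regimen 2 doses in cycles 5 and 6 (weeks 17 to 24), with no column in Table 1-8.

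**3. What general text still fixes after week 16.**

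| Item | Source outside the grid | Regimen 2 after week 16 |
|---|---|---|
| Dosing days | Table 1-1, Figure 1-10 notes, Section 6.1.2.1 | Defined for each cycle |
| Chemistry | Sections 6.1.4.1 and 6.2.2.2.4 | Defined on dosing days; not at end of treatment or follow-up |
| ECG | Table 1-9, Section 8.2.3.2 | Single rather than triplicate; days and hours undefined |
| Troponin, CK-MB, NT-pro-BNP | Section 8.2.5.3 (no timing), Table 1-9 (refers to the Schedule) | Undefined, including at end of treatment and follow-up |
| ECHO/MUGA | Section 8.2.3.4.2 | Defined at end of treatment and first long-term follow-up; on-treatment scans depend in part on a cardiac-marker rise |
| Pregnancy test | Section 8.2.5.4 | Defined each cycle, at end of treatment and at safety follow-up |
| Safety and long-term follow-up visits | Sections 8.1.4 and 8.1.5 | Visit timing defined; laboratory and cardiac-marker content is not |

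Table 1-9 asks sites to complete everything scheduled for the end-of-treatment and safety follow-up visits. For Regimen 2 that leads back to columns that do not exist.

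**4. Number of subjects.** Part 5B plans about 20 subjects, with the first 6 on Regimen 1 and the next 6 on Regimen 2. That leaves 20 − 6 − 6 = 8. Section 4.3 gives those places to Regimen 2 if it is deemed safe, while Figure 1-10 and Table 4-1 allow either regimen. The upper end is 6 + 8 = 14. The lower end is 0, because Section 1.1 opens Regimen 2 only if no safety issues arise after 6 subjects have enrolled in Regimen 1.

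**The case against.** A reader might infer that Regimen 2 has no cardiac, laboratory or ECG monitoring at all after cycle 4. The documents do not support that. Section 6.1.4.1 requires chemistry on AMG 176 dosing days. Section 6.2.2.2.4 says that renal chemistry and urinalysis "must be obtained and reviewed prior to each dose of AMG 176 per the schedule of assessments". Table 1-9 keeps a single ECG from cycle 5, and echocardiography and the follow-up visits have their own sections. This objection stands: what is missing is the grid of timepoints, not every requirement.

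Three further inferences also fail.

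- **Highest dose count.** Both Part 5B regimens give 7 doses per cycle. Regimen 2 is denser only in its 5 consecutive days, and in placing 7 doses within 9 days.
- **Loss of MRD data or of a comparison between regimens.** The marrow row in Table 1-8 continues before every other cycle until progression, Section 8.2.2.2.1 independently requires the central screening aliquot, and neither document plans a formal comparison of Regimens 1 and 2.
- **Missing rows.** Table 1-8 appears to lack the biomarker and central screening marrow rows of Table 1-7. The available text is a PDF conversion with displaced or lost cells, so this cannot be asserted. The blank ECHO/MUGA row has the same weakness.

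The conversion also means that the original page 3 should be looked at. Two separately titled pages with identical cycle and week headers make a pure conversion error unlikely.

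Finally, Section 2.3.1 cites a median survival under 3 months in this population, so few subjects might reach week 17. That limits the cycle 5 gap, but not the missing end-of-treatment and safety follow-up columns.

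**Conclusion.** The point holds as a schedule error with a bounded effect. Followed as written, Regimen 2 has no timepoints for troponin, CK-MB, NT-pro-BNP or ECG after week 16. It also has no specified laboratory or cardiac-marker content for the end-of-treatment, safety follow-up and long-term follow-up visits, apart from the pregnancy tests set elsewhere. The troponin rules in Section 6.2.2.1 presuppose such results.

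The exposure is 14 planned doses per subject who completes 6 cycles, in 0 to about 14 of roughly 20 Part 5B subjects. This assumes that page 3 reads in the original as it does here, and that the planned Part 5B numbers apply. SAP Section 10 reports early termination, and the documents do not say whether Regimen 2 enrolled anyone. If it did, the record should show what was collected after week 16 and at the closing visits. If it did not, the error matters only if the schedule is used again.

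**What to change.** Replace the repeated third page of Table 1-8 with one for cycle 5 onward, end of treatment, safety follow-up and long-term follow-up. Reconcile it with Tables 1-7 and 1-9 and with Sections 6.1.4.1, 6.2.2.2.4, 8.1.3 to 8.1.5, 8.2.3 and 8.2.5. The timepoints themselves are for the sponsor's clinical team to set; the need here is that these passages agree and that the Regimen 2 grid is complete.

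At the same time, check in the original table whether the biomarker and central screening marrow rows are really absent. If they are, reconcile the table with Section 8.2.2.2.1.

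The cost is one table page in an amendment. If no further amendment is planned and Regimen 2 enrolled, a short statement in the study report of what was collected after week 16 and at the closing visits would serve.
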